Implementation of a prehabilitation program will be feasible and will improve clinical status.

SPECIFIC AIMS

We propose to pilot (N=20) and assess a new prehabilitation program for frail surgical oncology patients. We will:

1. Assess feasibility. We will:
 - a. Evaluate adherence through analysis of patient maintained exercise logs.
 - b. Assess self-efficacy by evaluating the relationship between pre-program self-efficacy score and adherence.
 - c. Assess patient satisfaction and barriers to adherence through a post prehab program survey.

2. Assess clinical impact. We will:
 - a. Evaluate health-related quality of life before and after participation in the prehabilitation program.
 - b. Evaluate frailty before and after participation in the prehabilitation program.

METHODS

Study Design: Prospective cohort study

This longitudinal study will be a prospective, non-randomized, within-subject design focused on patients diagnosed with complex gastrointestinal (GI) cancer evaluated and treated at Maine Medical Center by the Surgical Oncology Service. All subjects who meet the inclusion criteria will be offered the opportunity to be enrolled; these recruitment efforts will cease when planned enrollment is complete. Participants will complete a prehabilitation exercise program through the Thinkific platform. Data on frailty, quality of life, self-efficacy and adherence will be collected through surveys and patient maintained exercise logs.

Study Population

Participants will be selected from the population of patients at the MMC Surgical Oncology Clinic. Patients at this clinic are being evaluated for surgical treatment of oncologic diseases such as colorectal or pancreatic cancer. Under normal circumstances, patients are seen for an initial consultation where a treatment plan is created. Patients either have surgery or chemotherapy up front. If the patient has surgery as the first treatment, the surgery is scheduled at that initial appointment. If the patient has chemotherapy before surgery, they will return for at least one more appointment after completion of chemotherapy. Their surgery is scheduled at this follow-up appointment. This process can span anywhere from 4 weeks to 6 months.

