Yearly, this clinic evaluates 181 and 143 patients with colorectal and pancreatic cancer, respectively. Part of the goal of this study is to evaluate feasibility as well as adherence and thus, patient tolerance of the prehabilitation program. Therefore, we propose to enroll 20 patients from this population, knowing that there may be some attrition. Participants will meet the following criteria:

Inclusion Criteria-

- a) Subjects ≥ 18 years old
- b) Evaluated at MMC by surgical oncology service
- c) Planned surgical intervention for gastrointestinal oncologic condition
- d) Score ≥ 40 on RAI frailty screening
- e) Physically able to participate in prehabilitation exercises
- f) Home internet access and established email account
- g) Able to speak and read the English language

Exclusion Criteria-

- a) Patients unable to participate in exercises included in prehabilitation program
- b) Patients with impaired decision making capacity as determined by the treating physician
- c) Those in a high risk community: prisoners and pregnant women

- d) Those who are visually impaired and unable to complete the course independently
- e) Those who do not meet the above inclusion criteria

[figure not shown]
Recruitment:

Patients are screened by nursing staff for frailty at each routine clinic visit using the RAI survey as part of their standard care. By reviewing the final RAI score obtained during the initial visit to the Surgical Oncology Clinic, the attending surgeon (see key personnel form) will know clinically if the patient is considered frail and therefore if he/she is eligible for inclusion in the research study. The attending surgeon will not need to go back to review the RAI score in-depth for research purposes. In addition to the RAI score, the attending surgeon will use inclusion/exclusion criteria to evaluate each patient’s eligibility for this pilot study. If the patient meets these criteria, the attending surgeon will give the patient a recruitment flyer (see attached) during the same visit to introduce the study requirements, expectations and possible benefits. The attending will answer any questions the patients may have at that time. No other recruitment, including active recruitment, will occur.

Informed Consent Process

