Repeat self-administered survey with the SF-36 will become available through a direct email link from REDCap at two and four weeks after initiation of the prehabilitation program. If participants do not complete the surveys, they will receive a reminder email, generated automatically by REDCap, at 24 and 48hrs after the initial email was sent (please see attached screen shot of emails). At the final clinic visit prior to surgery, the participant's exercise log will be collected by the study team. The participant's exercise log will either be physically brought to clinic or uploaded by the participant through the Thinkific platform prior to this final appointment. Repeat frailty screening, with the RAI, will be performed by the surgical oncology clinic nursing staff at every follow up clinic appointment until surgery as part of the patients' normal care.

Participants will complete a final self-administered SF-36 survey and a survey to assess their satisfaction with the exercise prehabilitation program anytime during the week leading up to their surgery, or the week after their final appointment if they ultimately are not a surgical candidate. The link to this final REDCap survey is embedded in Thinkific. The surgeon will remind patients at their final clinic visit to complete these surveys.

During the extent of the study, if patients have questions pertaining to the study they will be able to contact their surgeon at any time by contacting the surgical oncology clinic. If the patient has questions or concerns related to the performance of the prehabilitation program exercises, they will be directed to a licensed physical therapist.

Please reference to the attached material to view each of the following surveys:

Risk Analysis Index (RAI):

The RAI is a validated frailty screening tool that was developed and implemented at the University of Nebraska. Components of the RAI include nursing home admission, unintentional weight loss, renal failure, congestive heart failure, poor appetite, gender, shortness of breath, malignancy, age, cognition, and activities of daily living.²⁰

36-Item Short Form Survey (SF-36):

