performed as part of routine care will be initially recorded in Epic then manually transferred into REDCap.

Data from the SF-36, SEHEPS and satisfaction survey will be directly submitted into REDCap from either an emailed link or link embedded in Thinkific. Once uploaded, the participants formula ID (first two letters of first name + first two letters of last name) and email, will help us manually link the survey entry to the master list and the second survey data collection form. Of note, the participant will only enter their email and formula ID at the beginning of the first and last surveys. The email entry is necessary to send out the 2 week and 4 week surveys. The email will also serve as a second patient identifier if participants have identical formula IDs. When more than one survey is completed on the same day, the separate surveys are linked together through REDCap. This means the participants only need to type their formula ID and email once, despite completing multiple surveys. (please see the attached email chain and document from [name] regarding REDCap security and her support for this plan)

The exercise logs will be reviewed by the study team in Thinkific or through Epic, if the participant brought a paper log, then entered into REDCap. If participants bring a paper form of their exercise log, it will be scanned into their EPIC account by a member of the study team and the paper copy of the exercise log will be shredded after the image has been uploaded into Epic. The signed consent form will be secured in a locked file cabinet behind a locked office door in the Surgical Oncology Department at [name].

A master list will be maintained in REDCap separate from other study documents. Only a study ID, consisting of the first 2 letters of the first and last name, will link this master list to the two data collection files on REDCap. Once the data collection is finalized, the master list will be deleted. The limited data set that remains will then be exported as a CSV file that will be maintained as an encrypted file on a password protected MMC institution desktop. This limited dataset will be accessed only from MMC computers and only by MMC study team listed above and by members of the IRB if needed.

All regulatory documents and files associated with the study (IRB documents, HIPAA-related documentation) will be maintained for a minimum of 6 years after the final publication/report and then deleted/destroyed.

Data Analysis

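### The final SF-36 and the satisfaction survey are the only follow-up surveys with no stated emailed link or automatic reminders, so they are at higher risk of being missing or unlinkable

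*Combined protocol and SAP*

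**What the plan says.** All references are to the combined protocol and SAP.

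- **Aim 2a (Specific Aims):** "Evaluate health-related quality of life before and after participation in the prehabilitation program". The after time point is not named. Aim 1c covers satisfaction and barriers, by a survey after the programme.
- **Weeks 2 and 4 (Study Procedures):** the repeat SF-36 "will become available through a direct email link from REDCap at two and four weeks after initiation of the prehabilitation program". For non-responders, "they will receive a reminder email, generated automatically by REDCap, at 24 and 48hrs after the initial email was sent".
- **Final surveys (Study Procedures):** the last SF-36 and the satisfaction survey are due in the week before surgery, or in the week after the final appointment if there is no surgery. "The link to this final REDCap survey is embedded in Thinkific". The stated prompt is: "The surgeon will remind patients at their final clinic visit to complete these surveys".
- **Linkage (Data Management):** "the participant will only enter their email and formula ID at the beginning of the first and last surveys". Staff match entries manually from the name code and email, and email is named as the second identifier if two codes coincide. The same section later says "Only a study ID, consisting of the first 2 letters of the first and last name" connects the master list to the two data collection files. The master list is deleted once data collection is finalized.
- **Retention (Potential Problems):** the team will telephone participants who may have been lost, if needed, and staff are available for technical trouble.
- **Size (Study Population):** "we propose to enroll 20 patients from this population, knowing that there may be some attrition". The expected attrition is not quantified.

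**The concern.** The survey that matters most for the before-after comparison has the weakest delivery. Timeline gives a participation period of two weeks to six months, and only the final SF-36 is tied to its end. Week 4 falls mid-programme for a long participant and may fall after surgery for a short one. The satisfaction survey has no earlier administration to fall back on.

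Two things are at stake. The first is precision: with 20 enrolled, each lost or unlinked final survey removes a noticeable share of the pairs. The second is selection. A participant must return to Thinkific to answer questions about satisfaction with Thinkific, so those who disengaged are the least likely to reply. In a feasibility pilot their answers are the ones most needed.

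**Working it through.** The plan states no completion rate, linkage-error rate or precision target, so there is no figure of its own to reproduce. The check compares the procedures first, then gives illustrations on labelled assumptions.

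**Step 1. Procedures compared.**

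| | Weeks 2 and 4 | Final surveys |
|---|---|---|
| Route | Direct REDCap email | Link inside Thinkific |
| Automatic reminders | 24 and 48 hours | None stated |
| Personal prompt | None stated | Surgeon, at final visit |
| Identifiers typed by participant | No | Yes, code and email |
| General phone calls if lost | Yes | Yes |

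The asymmetry is confirmed. The surgeon's prompt also need not fall inside the survey window. Study Population says surgery-first patients have surgery scheduled at the initial appointment, and it describes a further appointment only for those having chemotherapy first. Study Procedures assumes a final visit before surgery, but nothing places it in the week before surgery.

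**Step 2. Precision if pairs are lost.** The 95% half-width for mean change, in SDs of the change, is t(0.975, n−1)/√n.

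- n = 20: 2.093/√20 = 0.47
- n = 16: 2.131/√16 = 0.53, wider by 0.533/0.468 = 1.14, or 14%
- n = 12: 2.201/√12 = 0.64, wider by 0.635/0.468 = 1.36, or 36%

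The values 16 and 12 are assumptions. The documents support no particular one.

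**Step 3. Selection.** If a fraction f is missing and the mean change in those observed differs by δ from that in those missing, the observed mean is off by f × δ. With 4 of 20 missing that is 0.2δ, and with 8 of 20 it is 0.4δ. The documents give no basis for δ.

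**Step 4. Linkage.** Assume each typed entry is wrong with probability e, independently, and compare the first survey with the last. One key disagrees with probability 1 − (1 − e)². Both keys disagree with the square of that.

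| e | One key disagrees | Expected of 20, code alone | Expected of 20, both keys | Chance of at least one with both |
|---|---|---|---|---|
| 2% | 0.0396 | 0.8 | 0.03 | 3% |
| 5% | 0.0975 | 2.0 | 0.19 | 17% |
| 10% | 0.19 | 3.8 | 0.72 | 52% |

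At modest error rates, failure of both keys is uncommon.

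**Step 5. Shared codes.** With K equally likely codes, the chance that at least two of 20 participants share one is 1 − ∏(1 − i/K), i = 0 to 19. This gives 32% at K = 500, 17% at 1,000, 9% at 2,000, 4% at 5,000 and 0.04% at 26⁴ = 456,976. The code is not unique by construction, but the answer depends almost entirely on K, which the documents do not give.

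**The case against.** A reader might infer that pairs will be lost or mis-linked, because matching rests on a non-unique name code. The documents do not support that. Matching uses email as well, and Data Management foresees identical codes and names email as the tie-breaker. The Step 5 figures are chances of a shared code, not of a wrong match, and a duplicate among 20 people would be visible on the master list. Even when both keys fail, the result is first an unlinked record, not a false link.

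A reader might also take the final SF-36 to be the declared end point. Aim 2a says only before and after. Data Analysis allows mixed models over time, which would still use week-2 and week-4 scores from someone with no final survey. That stands, although those scores do not measure status at the end of the programme and cannot replace the satisfaction survey.

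The phone calls and technical help are real mitigation aimed at disengaged participants. They are general and as needed, and are not a stated reminder for this survey. All comparisons are declared exploratory, so loss of power is not the argument; precision and selection are. Tying the prompt to the final visit is defensible because surgery dates vary. Finally, the email screenshots, REDCap security document, data collection document and phone script are not in the text reviewed and may add reminder or linkage steps.

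**Conclusion.** The point holds as a difference in risk. On the text reviewed, the final SF-36 and the satisfaction survey are the only follow-up surveys without a stated emailed link and automatic reminders, and they are linked by hand from retyped identifiers. They are more likely than the week-2 and week-4 surveys to be missing or unlinkable, above all for participants who have left Thinkific. Missingness is the stronger limb and failed linkage the weaker.

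The size cannot be derived from the documents; the losses in Step 2 are illustrative. This is an inexpensive improvement, not a defect that invalidates the pilot.

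Separately, Data Management is internally awkward: it relies on email as second identifier, yet says the name code alone links the master list to the data files. If email is not kept in those files, a duplicate code left unresolved when the master list is deleted could not be resolved later.

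**What to change.** 1. Send the final SF-36 and satisfaction survey by participant-specific REDCap email link, triggered from the entered surgery date or, if there is no surgery, the final-visit date. Use the same 24-hour and 48-hour reminders. Keep the Thinkific link and the surgeon's prompt as backup.
2. Assign a unique sequential study number at consent and use it, not name letters, as the linking key in the master list and both data collection files. With participant-specific links, no identifier has to be typed at the last survey.
3. Rewrite the two Data Management statements on linkage so that they agree on which identifiers are used and where email is held.

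The cost is REDCap configuration and a short revision of Study Procedures and Data Management. The emailing and reminder mechanism and the participants' addresses are already in use for weeks 2 and 4. The real burden is that the trigger is not a fixed interval from the start: staff must enter each participant's surgery or final-visit date and update it when it moves.

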After the account is created, participants will complete two electronic baseline surveys on an in room device during this initial clinic visit: the 36-Item Short Form Survey (SF-36) and the Self-Efficacy for Home Exercise Programs Scale (SEHEPS). The link for these REDCap surveys will be imbedded in Thinkific. A study team member will be available to assist in creation of the Thinkific account or completion of these initial surveys. Participants will leave their initial clinic appointment with a packet containing: a 3 pack of resistance bands, a copy of their consent form and a copy of the informational packet about the exercise program (see attached) that can otherwise be accessed through the Thinkific course.

Participants will additionally access the Thinkific account at home to complete an exercise based prehabilitation course. This course will provide video and written instruction on how to perform each exercise safely, as well as how to properly increase the intensity of the program, (e.g. resistance, number of repetitions and sets). This program will also include links to the American College of Surgeons alcohol related recommendations and the Maine QuitLink for tobacco/smoking and vaping cessation that patients may access if applicable. Participants will be instructed to perform daily exercise and keep track of their exercise in either a handwritten or electronic log (see attached document) until their surgery or until the final clinic visit if surgery is ultimately not performed. The log is available as a paper copy provided at the first visit and as a pdf embedded in the Thinkific course.

<https://mainehealth.thinkific.com/courses/prehab-exercise>

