Statistical analysis will be completed by the research fellow with support from CORE or statisticians. Data will be summarized using standard descriptive statistics. Continuous data will be shown as mean (standard deviation) or median [range], as appropriate, and categorical data will be shown as frequency (n, %). Paired analyses will be performed using the McNemar test for categorical data and the paired t test or Wilcoxon signed rank test for continuous data, as appropriate. Changes in survey scores over time will be assessed with repeated measures ANOVA or mixed models regression, as appropriate. Relationships among variables will be assessed by linear regression. "R" software will be used for data manipulation and all statistical analysis. As this is a pilot study, the parameters needed to support power analysis were not available. Therefore all statistical comparisons and relationships will be considered exploratory

with no anticipation of statistical significance. Statistical significance will be accepted at $p < 0.05$.

ANTICIPATED RISKS AND BENEFITS

The risks involved with participation in this study are low. One possible risk is for temporary muscular soreness. This is a risk for anyone starting a new exercise program. For those who experience it, the soreness is usually mild and can last for 24-72 hours following initial exercise sessions. Once the muscles become use to the new exercises, the soreness goes away. Further, participants will be able to contact a health care professional and a licensed physical therapist at any time during the study if they have questions or concerns. The program was explicitly designed for patient autonomy and independent use which is why the Thinkific instructions are very clear to guide the participant through every step. Despite this, patients are encourages to call with any questions. The number of phone calls will be tracked to assess the ideal program set up if implemented more widely in the future. Another risk is for loss of confidentiality. Many safeguards are in place to ensure that the data is protected including: use of REDCap for storage of the master list, password protection on the desktop of the PI and co-investigators, anti-virus software on desktops, and avoidance of use of mobile devices for storing data.

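### Aim 2 is an uncontrolled before-after comparison and cannot test the clinical half of the hypothesis; it should be framed and reported as descriptive

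*Combined protocol and SAP*

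**What the plan says.** The Hypothesis section states: "Implementation of a prehabilitation program will be feasible and will improve clinical status". Specific Aims puts the clinical half under Aim 2, headed as clinical impact. Aims 2a and 2b themselves are neutral: they evaluate quality of life and frailty before and after the program. Study Design describes one non-randomized cohort with within-subject comparison.

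Study Population says that "patients are seen for an initial consultation where a treatment plan is created" and that treatment starts with either surgery or chemotherapy. Surgery-first patients have surgery scheduled at that first appointment. For the others: "If the patient has chemotherapy before surgery, they will return for at least one more appointment after completion of chemotherapy". Eligibility does not restrict the pathway, and it requires an RAI score of at least 40.

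Under Study Procedures, "participants will complete two electronic baseline surveys on an in room device during this initial clinic visit", one of them the SF-36. It is repeated "two and four weeks after initiation of the prehabilitation program", and finally in the week before surgery, or in the week after the last appointment if there is no surgery. RAI is repeated by clinic staff at follow-up appointments until surgery.

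Data Analysis lists McNemar, paired t or Wilcoxon tests and linear regression, and adds: "Changes in survey scores over time will be assessed with repeated measures ANOVA or mixed models regression". No pathway or time-in-program term is named. It then says that "the parameters needed to support power analysis were not available. Therefore all statistical comparisons and relationships will be considered exploratory", and continues "with no anticipation of statistical significance. Statistical significance will be accepted at" p < 0.05.

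**The concern.** The hypothesis claims that the program causes clinical improvement. A before-after change in one group shows only that scores moved. Here at least three other things can move them: chemotherapy in part of the cohort, disease and time over very unequal intervals, and selection on a high baseline value of one of the outcomes.

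At stake is how the result is read. A p-value below 0.05 could be reported as support for the clinical claim, and a null or adverse change as evidence against it. Neither reading would be sound. Anticipated Risks and Benefits says that wide implementation is likely if the results support the hypothesis, so the reading matters beyond the pilot. Potential Problems lists loss to follow-up and technology, but not confounding.

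**Working it through.** The plan has no figure to reproduce: 20 is given without a power or precision calculation, and Data Analysis says that the inputs were not available. The check is therefore mainly one of structure.

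**1. What the interval contains.**

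| | Surgery-first | Chemotherapy-first |
|---|---|---|
| Baseline SF-36 and RAI | Initial visit | Initial visit |
| Between baseline and final SF-36 | Wait for surgery | Chemotherapy, then wait for surgery |
| Return appointment stated in Study Population | None | At least one, after chemotherapy |
| Final SF-36 | Week before surgery | Week before surgery |

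Timeline gives program time as typically two weeks to six months. With six months taken as 26 weeks, 26 / 2 = 13-fold. Study Population gives 4 weeks to 6 months for the clinic process, which is 26 / 4 = 6.5-fold. The interval is very unequal on either figure. The two- and four-week SF-36 surveys are at a common time from program start, but their relation to chemotherapy is not stated.

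**2. What the pooled change estimates.** Let P be the program effect, C the extra change over a chemotherapy period, s the chemotherapy-first share, T the change from disease and time, and R regression to the mean (for RAI).

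- Pooled mean change = P + sC + T + R.
- Surgery-first change = P + T + R.
- Chemotherapy-first change = P + C + T + R, even if P, T and R are taken as equal across pathways.

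The pooled figure is one number with several unknowns. The difference between pathways gives C, not P. Splitting by pathway therefore makes the mixture visible but does not isolate the program effect. The documents give neither s nor C, so the direction of bias is unknown.

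**3. Regression to the mean in RAI.** Assume a normal RAI distribution, a cutoff of 40 lying c SD above the clinic mean, and test-retest correlation r. With no program effect, the expected fall is (1 − r) × φ(c) / [1 − Φ(c)] SD.

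- c = 0.5, r = 0.9: 0.1 × 1.141 = 0.11 SD.
- c = 2, r = 0.7: 0.3 × 2.373 = 0.71 SD.

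In simulation (n = 20, 20,000 runs per setting, c from 0.5 to 2, r from 0.7 to 0.9), a two-sided paired t test at 0.05 showed significant improvement in 19% to 99% of runs, against a nominal 2.5%. Both c and r are assumed. The range shows only that the effect can be large enough to matter.

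**4. Precision of a split by pathway.** The 95% confidence interval half-width, in SD of change, is t(0.975, n − 1) / √n.

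- n = 20: 2.093 / 4.472 = 0.47.
- n = 10: 2.262 / 3.162 = 0.72.
- n = 5: 2.776 / 2.236 = 1.24.

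The sizes 10 and 5 are assumed; the documents give no pathway split and no attrition figure.

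**The case against.** The strongest reply is that the plan has largely dealt with this. It is openly a pilot, it says that it is non-randomized, Aims 2a and 2b claim no effect, and every comparison is exploratory whatever the reason given for the label. Lack of a control is common to all single-arm pilots. Most of this stands, and it limits the point to wording, analysis framing and reporting. It does not close it. The stated ground for the label is missing power parameters, and better power would not separate program from chemotherapy, time or selection. The label is also followed at once by an acceptance rule, while the hypothesis stays causal.

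A reader might infer that p < 0.05 on Aim 2 is the trigger for roll-out. The documents do not say so: implementation is tied to the hypothesis as a whole, which includes feasibility, and the background cites existing perioperative recommendations as separate grounds for adoption.

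It is also fair to object that a pathway breakdown in 20 patients is imprecise and does not cure the attribution problem. That stands in full. Its purpose is only to show what was pooled. Pathway may already be recorded, since the data collection document is an attachment not in the text; what is absent is a stated analysis that uses it.

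**Conclusion.** The point holds as a matter of attribution. Aim 2 can describe change in quality of life and frailty during the program; it cannot support or refute the claim that the program improves clinical status. Three features of this protocol make that more than the usual single-arm caveat: chemotherapy falls inside the interval for one pathway only, program time varies about 13-fold, and patients are selected on RAI, which is then an outcome.

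The size of the bias cannot be derived from the documents. The regression-to-the-mean figures rest on an assumed cutoff position and correlation, and the pathway precision figures on assumed group sizes. It would go too far to say that an observed change must be spurious, or that pooling biases it in a known direction. The feasibility aims are unaffected.

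**What to change.** 1. **Hypothesis and Specific Aims.** Restate the clinical part of the hypothesis and the Aim 2 heading as describing change in quality of life and frailty during the program. State that change cannot be attributed to the program because there is no control, treatment pathways are mixed, and patients are selected on RAI of at least 40.
2. **Data Analysis, Aim 2 only.** Drop the p < 0.05 acceptance rule. Make mean change with 95% confidence interval the main result, and label any p-values from the paired tests, ANOVA or mixed models as descriptive. Show change overall and descriptively by pathway, defined from the plan made at the initial consultation, with the number contributing and time since baseline. Note that follow-up RAI may be sparse in surgery-first patients, for whom Study Population states no return appointment, and that pathway estimates are imprecise and do not isolate the program effect. The table layout can be left to the study team.
3. **SF-36 timing.** Flag any two- or four-week survey completed after surgery and leave it out of the pre-surgery change. The program can be as short as two weeks, and Study Procedures states no stop of the emailed surveys at surgery.

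The cost is rewording, a few table rows and at most one added data field for pathway. No visit, survey or participant is added.
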